8.4.1.2 Serious Adverse Events

The primary safety parameter in this study is the incidence and severity of serious adverse events (SAEs).

Incidence and frequency of treatment emergent SAEs will be summarised by system organ class (SOC) and preferred term (PT):

- overall,
- by maximum severity,
- by maximum relationship to treatment
- treatment related SAEs.

In each table, if the same SOC or PT is reported on multiple occasions for a single subject, it will be included only once in the summary. In the table by maximum severity, only the most severe occurrence for each SOC and PT for each subject will be included in the summary. In the table by relationship, only the most related occurrence for each SOC and PT for each subject will be included in the summary.

Any SAEs that are not treatment emergent (occurred prior to the infusion) will be listed.

If there are any deaths, the details will be listed.

8.4.1.3 Adverse Events

Treatment emergent adverse events will be summarised in an overall summary presenting the number (%) of subjects with:

- any AE,
- AE grade 2 or higher (at least moderate in severity),
- AE grade 3 or higher (at least severe in severity),
- treatment related AE,
- AE leading to study withdrawal,
- any serious adverse event (SAE),
- treatment related SAE,
- SAE leading to death.

Incidence and frequency of treatment emergent AEs will be summarised by system organ class (SOC) and preferred term (PT):

- overall,
- by maximum severity,
- by maximum relationship to treatment,
- treatment related AEs,

Final Version 4.0 Page 23 of 27

AEs leading to study withdrawal (if sufficient events).

In addition, a summary table for the most frequently reported treatment emergent adverse events (those reported in 2 or more subjects) will be presented by PT in descending order of incidence and frequency.

In each table, if the same SOC or PT is reported on multiple occasions for a single subject, it will only be included once in the summary. In the table by maximum severity, only the most severe occurrence for each SOC and PT for each subject will be included in the summary. In the table by maximum relationship, only the most related occurrence for each SOC and PT for each subject will be included in the summary.

Any adverse events that are not treatment emergent (occurred prior to the infusion) will be listed.

8.4.2 Concomitant Medications

Concomitant medications taken during the study will be listed.

8.4.3 RCL Testing

Number (%) of OTL-101 treated subjects testing positive for RCL will be summarised by visit and at any time.

8.4.4 Laboratory Evaluations

8.4.4.1 Haematology

Haematology parameters (red blood cell (RBC) count, haemoglobin, haematocrit, mean corpuscular volume (MCV), mean corpuscular haemoglobin (MCH), mean corpuscular haemoglobin concentration (MCHC), white blood cell (WBC), neutrophils, lymphocytes, monocytes, eosinophils, basophils and platelet count) will be evaluated over time for the OTL-101 treated subjects. The baseline evaluation for each parameter will be the final evaluation prior to the OTL-101 infusion.

For each parameter, the actual value and change from baseline will be summarised at each visit using descriptive statistics.

Haematology evaluations will be flagged against the normal range as low/normal/high. For each parameter, the number (%) of subjects with evaluations that were low/normal/high relative to the normal range will be summarised by visit. In addition, shift tables will be constructed comparing the flags at the baseline evaluation with those at each post-infusion evaluation and the minimum and maximum evaluation post-baseline. Out of range values will be assessed for their clinical significance. The number (%) of subjects with any clinically significant abnormal values will be summarized by visit and at any time post-infusion.

Final Version 4.0 Page 24 of 27

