4.2 Study Endpoints

4.2.1 Primary Endpoints

4.2.1.1 Evaluation of Safety

Primary Endpoint: Incidence and grade of Serious Adverse Events (SAE).

Serious adverse events may be manifest as:

- a) clinical toxicities
- b) exposure to replication-competent lentivirus (RCL)
- c) development of monoclonal expansion or leukoproliferative complications from vector insertional effects.

a) To detect potential clinical toxicities from the treatment, patients will have interval medical histories taken, complete physical examinations, and phlebotomy to obtain peripheral blood for laboratory studies on day +1, and then at months 1, 2, 3, 4, 5, 6, 8, 10, 12, 15, 18, 21 and 24 (+/- 4 weeks). Laboratory studies performed at these time-points will include CBC with differential and platelet count and a chemistry panel and electrolytes. Toxicities relative to the clinical parameters, the CBC with differential, and the chemistry panel are defined by an adapted Pediatric Clinical Toxicity Scale from the NIAID, Division of AIDS. ([Appendix G](#))

Patients will also be monitored by clinical examination and laboratory studies in the immediate period (3 to up to 6 weeks, depending on clinical course) after infusion of OTL-101 to monitor myelosuppression expected from the administered busulfan.

b) To detect exposure to replication-competent lentivirus:

i. PBMC will be assayed by PCR to detect RCL. This test will be performed by the National Gene Vector Biorepository on samples obtained at baseline (pre-infusion), 3, 6, 12 and 24 months post-infusion. Samples will also be collected annually thereafter, and cells archived for PCR assay, to be run if any samples are positive.

ii. Serum for measurement of antibody to RCL will be archived for the presence of antibody to VSV-G envelope at baseline (pre-infusion), 3, 6, 12 and 24 months post-infusion (and annually thereafter).

c) To monitor for monoclonal expansion or leukoproliferative complications, LAM-PCR will be performed, as described in [Appendix F](#).

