9.4 Methods and Timing for Assessing, Recording, and Analyzing, Managing Safety Parameters

9.4.1 Methods and Timing for Assessment

Following the infusion of the gene-modified cells (study agent), the subject will visit a clinical investigator at the following time points: day 1, months 1, 2, 3, 4, 5, 6, 8, 10, 12, 15, 18, 21, and 24. At each time point, a history (solicited) and physical exam and phlebotomy (unsolicited) for lab tests will be performed. The notes of the history and results of the physical and lab tests will be used to determine adverse event. Notes and results will be recorded on case report forms (CRFs). Any physical and medical condition and lab value outside of normal parameters will be noted and compared to the NIAID Pediatric AIDS Toxicity Table ([Appendix G](#)) to determine the grade of the abnormal parameter. In years 3-15, subjects will continue to be followed, albeit less often (1-2 times/year), for IO monitoring. The IO monitoring plan is given in [Appendix F](#).

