9.9 Halting Rules for the Protocol

If any one of the following five instances occurs, new enrollment to the protocol or treatment of subjects will be halted, pending investigation of the cause. Findings will be discussed with the FDA, IRB and DSMB and each must agree to conditions by which the study can be resumed before enrolling the next patient. Evaluations of study endpoints of subjects already enrolled and who received the final cell product will continue to be performed.

1. If there is one death or four grade 4 toxicities (except grade IV busulfan-related hematologic serious adverse events {transient leukopenia, anemia, thrombocytopenia resolving within 42 days of transplant} which are anticipated and will be reported, but will not be considered stopping

criteria). Additionally, neutropenia (a documented disorder of ADA-deficiency) occurring at any time, will be graded for severity but will not count towards the stopping rule.

2. If two subjects have prolonged unresponsive pancytopenia. This is defined as initial failure at hematologic reconstitution which does not improve following administration of the back-up marrow. Failure of hematologic reconstitution is defined as at least any two of the following being: ANC $<200/\text{mm}^3$, and/or platelets $< 20,000/\text{mm}^3$ without transfusions, and/or Hb $< 8.0 \text{ gm/dl}$ without transfusions) on three independent and consecutive determinations over at least ten days beyond day +42 from initial infusion of the cell product. If these conditions are reached, the back-up marrow will be infused IV. If failure of hematologic reconstitution persist after the back-up marrow has been given through day +90 from the initial infusion of the cell product, prolonged unresponsive pancytopenia will exist.

3. If 0 of 3 successive patients show evidence of engraftment of transduced cells by six months of follow-up (all peripheral blood samples negative by ddPCR/qPCR for vector sequences ($<1/10,000$) or by ADA enzyme assay).

4. If RCL is detected, and confirmed in one subject.

5. If a subject in this study develops hematological proliferative, monoclonal expansion or malignant disease (excluding DFSP). A thorough investigation of the cause of the proliferation, expansion or malignancy, including proviral integration analysis, will be done.

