*For female subject of child-bearing potential

aincludes albumin, AST/ALT, alkaline phosphatase, total protein, total bilirubin, creatinine, BUN, glucose, calcium, Na+, K+, Cl-, total CO2

bincludes lymphocyte subsets phenotype, quantitative immunoglobulins, antibodies to Tet/PRP (Q 3 months if not receiving IVIg), T cell proliferation to PHA/Tet (only at 6, 12, 18, and 24 months and only to Tet if immunized against tetanus).

^cAt each time, any unused PBMC will be cryopreserved in liquid nitrogen, for possible future studies.

^dTo be banked for possible future studies

^eBusulfan PK at 0, 1, 2, 4, 8, 13 hours following IV Busulfan administration, done during hospitalization

^fMyelosuppression Laboratory: Hepatic function tests, CBC/Diff, 2x per week for up to 6 weeks, from day +1 until hospital discharge when neutrophil recovery is observed, or longer as indicated. For subjects who have slow recovery of counts after transplant (beyond Day +30), CBC/Diff will be performed at least once every 7-10 days until ANC is >500 cells/mm.³

gAccording to current FDA guidelines, LAM-PCR samples will be obtained ≈ every 6 months, for 5 years, then annually for an additional 10 years

Final Version 4.0 Page 9 of 27

4 Study Objectives

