7.2 Safety Population

The safety population will consist of all subjects treated with OTL-101 at UCLA/NIH (current study cohort) and the complete HSCT historical control cohort consisting of ADA-SCID patients with any type of donor treated with HSCT at either GOSH or Duke University from the year 2000 onwards.

8 Statistical Methods

In general, continuous variables will be summarised using the mean, standard deviation, median, minimum, maximum and number of subjects. Categorical variables will be summarised using number of subjects and percentages.

For all summaries, the HSCT controls will be summarised in the groups of those without a matched related donor, those with a matched related donor and all subjects.

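### The laboratory safety tables carry no toxicity grade, no time to or duration of count recovery, and no split at the protocol's day +42 line between anticipated and prolonged cytopenia

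*SAP*

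**What the plan says.** SAP 8.4.4.1 plans four things for each haematology parameter.

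- Values: "For each parameter, the actual value and change from baseline will be summarised at each visit using descriptive statistics". The opening of SAP section 8 says that "continuous variables will be summarised using the mean, standard deviation, median, minimum, maximum and number of subjects", so the lowest count at each visit is printed.
- Flags: "Haematology evaluations will be flagged against the normal range as low/normal/high", counted by visit.
- Shift tables: the baseline flag against "those at each post-infusion evaluation and the minimum and maximum evaluation post-baseline".
- Clinically significant abnormal values, by visit and at any time after infusion.

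SAP 8.4.4.2 does the same for biochemistry. SAP 8.4.1.2 and 8.4.1.3 tabulate serious and all adverse events by maximum severity, with one worst occurrence per term per child.

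The protocol treats these data differently. Under 4.2.1.1, toxicities for "the CBC with differential, and the chemistry panel are defined by an adapted Pediatric Clinical Toxicity Scale". Under 9.4.1, any "lab value outside of normal parameters will be noted and compared to the NIAID Pediatric AIDS Toxicity Table" to obtain a grade. Section 9.9 exempts from the grade 4 count busulfan-related "transient leukopenia, anemia, thrombocytopenia resolving within 42 days of transplant". Its second halting rule concerns pancytopenia on three consecutive determinations over at least ten days beyond day +42 that persists after the back-up marrow.

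Footnote f to the schedule in SAP section 3 sets extra monitoring after busulfan: "Hepatic function tests, CBC/Diff, 2x per week for up to 6 weeks". Slow recoverers then have counts at least every 7-10 days.

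**The concern.** Marrow suppression is an expected acute effect of the busulfan conditioning. The useful safety questions are how deep it went, how long it lasted, and whether it came back or never resolved. Prolonged unresponsive pancytopenia is a halting event (Protocol 9.9), and cytopenia is a screening signal for clonal expansion (Appendix F).

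The protocol collects data for these questions: graded values, frequent counts to week 6, and further counts for slow recoverers, which the protocol's change list attributes to a request from the data and safety monitoring board. The SAP has no output that matches them. SAP 8.3.2.6, headed Engraftment, covers vector marking only. If the tables stay as planned, the report can say how many children were low at a visit and how many ever had a severe event. It cannot say, from a planned table, how many had an ordinary busulfan course and how many had prolonged or recurrent cytopenia.

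**Working it through.** The plan states no figure on this point, so there is none to reproduce. The check compares what each planned table can show with what the protocol distinguishes.

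**1. Grade.** Protocol 4.2.1.1 and 9.4.1 grade out-of-range counts and chemistry values, and 9.9 adds that neutropenia will be graded for severity. SAP 8.4.4.1 and 8.4.4.2 contain no grade. In the flag and shift tables, a neutrophil count just under the lower limit and a count of 0 fall in the same cell.

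**2. Visit windows against day 42.** Inputs: 13 visits at months 1, 2, 3, 4, 5, 6, 8, 10, 12, 15, 18, 21 and 24, each ±4 weeks (Protocol 8.4 and Appendix B). Window = month × 365.25/12 ± 28 days.

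| Visit | Centre (day) | Window (days) | Against day 42 |
|---|---|---|---|
| Month 1 | 30.4 | 2-58 | straddles |
| Month 2 | 60.9 | 33-89 | straddles |
| Month 3 | 91.3 | 63-119 | wholly after |
| Months 4 to 24 | 121.8 and later | start at day 94 or later | wholly after |

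So 13 − 2 = 11 visits cannot contain a value from the first 42 days. Months 1 and 2 can fall on either side and overlap each other from day 33 to day 58.

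**3. The minimum post-baseline shift.** One minimum is taken over all follow-up. A child who is low only at the early nadir and a child who is low then and again a year later both appear as low, once.

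**4. Persistence.** The second halting rule needs three consecutive determinations in one child. A group minimum per visit does not show whether the same child stayed low.

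**5. Adverse event tables.** Each child contributes the worst occurrence of each term, with no time window. If a child has grade 4 neutropenia before day 42 and again after it, the table shows one grade 4 event and does not say when.

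**6. Interim counts.** Twice weekly for six weeks is 2 × 6 = 12 counts at most, against two scheduled visits (day +1 and month 1) nominally in that span. Twelve is a ceiling, because monitoring may end at discharge once neutrophils recover. The SAP does not say whether these counts enter the shift to each post-infusion evaluation.

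**7. How saturated the minimum column would be.** The documents give no rate. Let p be the assumed probability that a child is ever low, with P(X ≥ 18) = Σ C(20,k) p^k (1−p)^(20−k) for k = 18 to 20.

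| p | Expected low (20p) | P(at least 18 of 20 low) |
|---|---|---|
| 0.70 | 14 | 0.035 |
| 0.80 | 16 | 0.206 |
| 0.90 | 18 | 0.677 |
| 0.95 | 19 | 0.925 |
| 0.99 | 19.8 | 0.999 |

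The column is uninformative only if p is about 0.9 or more.

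**The case against.** A reader might infer that haematology is reduced to flags plus one worst value. The documents do not support that. SAP 8.4.4.1 also gives actual values and changes by visit, shifts to each evaluation, and clinical significance by visit.

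A reader might also infer that late cytopenia cannot be seen at all. That fails too: from month 3 onward a low count at a visit cannot be the early nadir.

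A third tempting reading is that nearly every child will be low, or that most of the busulfan counts are lost. Both are assumptions. The lymphopenia criterion in Protocol 5.1.1 is one of several alternatives and refers to the time before immune restorative therapy. Platelets below 150,000 were excluded at entry, so baseline status does not saturate the platelet shift.

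It can further be said that grading runs through adverse events. The form records maximum toxicity with onset and resolution dates (Protocol 9.4.2), grade 3 or higher is tabulated, subject listings are promised (11.6.1), and stopping criteria are reviewed quarterly (14.5). The primary safety endpoint is serious adverse events, not a laboratory shift table. Neutropenia at any time is exempt from the first halting rule.

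All of this stands, and it limits the size of the point. It does not close the gap. The severity tables have no timing, clinical significance is a judgement without stated criteria, and reconstructing a course by hand from listings is not a planned analysis.

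**Conclusion.** The point holds as a reporting gap in the safety analysis. The SAP plans no graded laboratory table, no time to or duration of count recovery, and no separation at the protocol's own day +42 line. Months 1 and 2 straddle that line, the overall minimum pools the nadir with later values, and the severity tables can let an expected early grade 4 hide a later one in the same child.

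The loss concerns depth by period, duration and recurrence. It does not concern detection of cytopenia present at month 3 or later visits. Grade 4 events should also appear in the adverse event tables, but without timing and only if graded laboratory values are recorded as adverse events, which Protocol 9.4.1 implies without stating it for every value. No number of affected children can be given, because the documents report no cytopenia rates.

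**What to change.** **First, settle the definitions.**

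- Protocol 4.2.1.1, 9.2, 9.4.1 and 9.4.1.1 grade on the NIAID paediatric table, while 11.3.1 names CTCAE. These must be reconciled.
- Appendix G is titled for children over 3 months, while enrolment starts at 1 month. State how younger children are graded.
- Neutrophil recovery is worded as consecutive days in Protocol 6.3 and consecutive measurements in 7.4. The passages must be reconciled.

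**Then add to the SAP.**

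- In 8.4.4.1, and in 8.4.4.2 for liver tests: shift tables from baseline grade to worst grade, shown separately for infusion to day 42 and after day 42.
- In 8.4.1.2 and 8.4.1.3: the cytopenia severity tables split at day 42, with events that begin by day 42 and continue past it shown as such.
- Where the twice-weekly counts are in the database: per-child nadir neutrophils and platelets, time to recovery, and days below each of the protocol's existing thresholds, noting transfusion support where recorded.

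Keep the by-visit summaries.

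**Cost.** A few more safety tables for 20 children, mainly programming, and no change to patient procedures. Some data checking is needed. The documents schedule the interim counts but do not say that they are entered on the case report form, and children transferred to a home physician after three days may have gaps. If the counts are missing, the graded and split tables can still be built from scheduled counts and adverse event dates, and the limitation should be stated.

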8.4.4.2 Biochemistry

Study: NCT01852071 - UCLA Fresh

Biochemistry parameters (Urea Nitrogen, creatinine, total bilirubin, sodium, potassium, chloride, calcium, aspartate aminotransferase (AST), alanine aminotransferase (ALT), alkaline phosphatase, albumin, total protein, glucose, magnesium, phosphorus, total CO2) will be evaluated over time for the OTL-101 treated subjects. The baseline evaluation for each parameter will be the final evaluation prior to the OTL-101 infusion.

For each parameter, the actual value and change from baseline will be summarised at each visit using descriptive statistics.

Biochemistry evaluations will be flagged against the normal range as low/normal/high. For each parameter, the number (%) of subjects with evaluations that were low/normal/high relative to the normal range will be summarised by visit. In addition, shift tables will be constructed comparing the flags at the baseline evaluation with those at each post-infusion evaluation and with the minimum and maximum evaluation post-infusion. Out of range values will be assessed for their clinical significance. The number (%) of subjects with clinically significant abnormal values will be summarized by visit and at any time post-infusion.

8.4.5 Vital Signs, Height and Weight

Vital signs (temperature, heart rate, respiratory rate, systolic and diastolic blood pressure), height and weight are measured over time for the OTL-101 treated subjects.

The baseline evaluation for each of the vital signs, height and weight will be the final evaluation prior to the OTL-101 infusion.

For each parameter, the actual value and change from baseline will be summarised at each visit using descriptive statistics.

Each subject's vital signs be categorized as normal, abnormal not clinically significant or abnormal clinically significant at each visit. The number (%) of subjects with clinically significant evaluations will be summarised by visit and at any time post-infusion.

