1 OVERVIEW

1.1 Protocol Summary

Full Title	Autologous Transplantation of Bone Marrow CD34+ Stem/Progenitor Cells after Addition of a Normal Human ADA cDNA by the EFS-ADA Lentiviral Vector for Adenosine Deaminase (ADA)-Deficient Severe Combined Immunodeficiency (SCID)
Short Title	Lentiviral Vector ADA Gene Transfer for ADA-Deficient SCID
Clinical Trial Phase	I/II
IND Sponsor	Orchard Therapeutics, Ltd.
Conducted By	University of California, Los Angeles and the National Institutes of Health
[REDACTED]	[REDACTED]
Sample Size	n=20
Study Population	Children older than 1.0 months who have ADA-deficient SCID
Accrual Period	5 years
Study Design	This is a controlled, prospective, non-randomized Phase I/II clinical trial to assess the safety (as primary end-point) and efficacy (as secondary endpoints) of autologous transplantation of CD34+ cells from the bone marrow (BM) of ADA-deficient SCID infants and children following human ADA cDNA transfer by the EFS-ADA lentiviral vector. Following provision of informed consent, enrolled subjects will be screened to determine full eligibility for participation over 1-2 weeks. Eligible subjects will be admitted to undergo harvesting of autologous BM under general anesthesia, with placement of a central venous access line, if not already present. If sufficient BM cells were collected to cryopreserve a “back-up sample” of at least 5×10^7 total nucleated cells/kg (or 3×10^7 mononuclear cells/kg) and also yield $\geq 1 \times 10^6$ CD34+ cells/kg, the CD34+ cells will be cultured for EFS-ADA lentiviral vector-mediated transduction. The subjects will receive a single dose of busulfan (4 mg/kg) IV. At the end of transduction, the final cell product (autologous BM CD34+ cells transduced with the EFS-ADA lentiviral vector, OTL-101) will be assessed to determine if it meets release criteria, and if so, it will be infused IV. For subjects who have successfully received the final cell product, PEG-ADA ERT will be stopped at day +30 after transplant. The initial portion of the study will require the subject to be treated in the hospital for a typical duration of 10 days-6 weeks. After discharge from the hospital, the subject will be seen for interval history and examination by either their home physician, the PI or a CI and have blood

[figure not shown]

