2.1.2 Adenosine deaminase (ADA)-deficient SCID

Severe combined immunodeficiency (SCID) has been recognized for over four decades as an inherited disorder in which patients have profoundly defective immunity with essentially no T lymphocyte function and minimal to absent B cell function ([Kohn and Weinberg, 1996](#); [Buckley, 2004](#)). SCID patients typically present for medical attention between 3-9 months of age with multiple, recurrent severe infections with common childhood pathogens (encapsulated bacteria, respiratory syncytial virus, parainfluenza virus) or opportunistic organisms (*Candida albicans*, *Pneumocystis jirovecii*, cryptococcus). Related findings often include failure to thrive and wasting, persistent diarrhea, and delayed growth and dentition.

The clinical syndrome of SCID is due to a variety of specific genetic lesions, each of which impairs normal T cell development and function. The first specific genetic cause of SCID to be identified was deficiency of the enzyme adenosine deaminase (ADA) ([Giblett et al, 1972](#)). It is estimated that ADA deficiency accounts for 15-20% of cases of SCID. Other known genetic lesions resulting in SCID include: mutations in the IL-2 receptor gamma chain (γ_c), (responsible

for X-linked SCID); defects in Jak3 kinase and other components of T cell intracellular signaling pathways; the inability to produce interleukin-2 (IL-2); defects in components of the T cell antigen receptor complex; defects in the recombinase system which is responsible for rearrangement of immunoglobulin and T cell receptor genes; and impaired expression of HLA antigens (bare lymphocyte syndrome). Once a definitive diagnosis of ADA deficiency is made, patients may be treated with a hematopoietic stem cell transplant (HSCT), which includes HLA-identical matched sibling donor bone marrow transplant (BMT) or haplo-identical parental T cell-depleted BMT, or in some cases a matched unrelated adult donor BMT or matched unrelated cord blood HSCT. However, if a matched sibling donor is unavailable, most ADA-deficient patients are treated with ADA enzyme replacement therapy (ERT). These treatment options and outcomes are discussed in detail below.

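### Height and weight are summarised only as raw values and raw change from baseline in growing children, so growth faltering or catch-up is hard to detect in that table

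*SAP*

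**What the plan says.** SAP 8.4.5 is part of the safety evaluations and covers the OTL-101 group only: "height and weight are measured over time for the OTL-101 treated subjects". Its baseline rule is "The baseline evaluation for each of the vital signs, height and weight will be the final evaluation prior to the OTL-101 infusion", and its summary rule is "For each parameter, the actual value and change from baseline will be summarised at each visit using descriptive statistics". The general rule at the start of SAP Section 8 defines the statistics: "continuous variables will be summarised using the mean, standard deviation, median, minimum, maximum and number of subjects".

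The one clinical classification in 8.4.5 is worded for vital signs: "Each subject's vital signs be categorized as normal, abnormal not clinically significant or abnormal clinically significant at each visit". The section lists height and weight separately from the vital signs, so the classification does not cover them as written. No z-score, centile, growth velocity, growth reference or faltering threshold appears in the SAP or in the protocol text available.

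On the population, the Protocol Summary (1.1) gives "Children older than 1.0 months who have ADA-deficient SCID", SAP Section 1 extends the description to adolescents, and follow-up is 24 months. Protocol 2.1.2 lists among the findings at presentation of SCID "failure to thrive and wasting, persistent diarrhea, and delayed growth and dentition".

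The SAP does use references for other measures. Individual plots of immunoglobulins (8.3.2.2) and lymphocyte subsets (8.3.2.4) carry age-dependent normal ranges. Haematology and biochemistry (8.4.4) are flagged low, normal or high, with shift tables.

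**The concern.** A raw change is informative when the expected change is near zero, as for temperature or sodium. For height and weight in children the expected change is positive and depends strongly on age. A child can drop well below the expected track and still contribute a gain. A child who catches up after failure to thrive contributes a larger gain, which cannot be told apart from ordinary growth at a younger age.

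Pooling makes this worse. If every child stayed exactly on the reference median, the mean raw change would still be the average of the age-specific expected gains. It would therefore move with the age mix alone.

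What is at stake is the readability of one safety table, in a disease whose presentation includes poor growth. Protocol 2.3.1 also says that the toxicity of low-dose busulfan in a paediatric population is not known. Harm and recovery in growth would both be of interest, and the table separates neither from normal ageing.

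**Working it through.** The documents state no figure on height or weight, so there is nothing to reproduce. The check is algebra with assumed inputs.

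**From the documents:** N = 20 (Protocol 11.4); entry from 1 month of age; adolescents included; 24 months of follow-up; raw value and raw change only.

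**Assumed:** a child at z-score z has a value of about M(1 + CV·z), where M is the reference median for age and sex. The coefficient of variation (CV) is 10%, 12% or 15% for weight and 4% for height. M1 and M2 are the reference medians at baseline and at the visit, and r = M2/M1.

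**Step 1: when faltering still shows as a gain.** A child moves from z = 0 to z = -2.

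- Raw change = M2(1 - 2·CV) - M1.
- This is positive when r > 1/(1 - 2·CV).
- Weight, CV 10%: 1/0.80 = 1.25.
- Weight, CV 12%: 1/0.76 = 1.32.
- Weight, CV 15%: 1/0.70 = 1.43.
- Height, CV 4%: 1/0.92 = 1.09.

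A two-SD fall in weight is thus recorded as a gain once the reference median has risen by more than about 25-43%. For height the figure is about 9%.

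**Step 2: size of the recorded change.** As a percentage of baseline, the change is 100·[r(1 - 2·CV) - 1].

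| r | Child who stays at z = 0 | Child who falls to z = -2 (CV 10%, 12%, 15%) |
|---|---|---|
| 2.0 | +100 | +60, +52, +40 |
| 1.5 | +50 | +20, +14, +5 |
| 1.25 | +25 | 0, -5, -12.5 |
| 1.15 | +15 | -8, -12.6, -19.5 |

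Masking is strong where growth is fast, as in infants. Where growth is slow, as in older children, the same fall shows as no gain or as a loss.

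**Step 3: effect on the mean.** Take 20 children with the same baseline median, r = 2.0 and CV 12%. If 4 fall from z = 0 to z = -2, the mean raw change is (16 × 100 + 4 × 52)/20 = 90.4% of baseline, against 100% if none falls. Every child still shows a gain. On the z scale the mean change is 4 × (-2)/20 = -0.40 and the minimum is -2. If all 20 fall, the mean raw change is still +52%.

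**The case against.** A reader might infer that every child would appear to improve, or that growth faltering could not be seen at all. The documents support neither.

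- A child who loses weight has a negative change, and the minimum is among the planned statistics. Step 2 shows that slower-growing older children can show a loss. The SAP also nowhere labels a gain as improvement.
- Other routes exist. Protocol 9.4.1 has physical and medical conditions outside normal limits noted and graded. SAP 8.4.1.3 tabulates treatment-emergent adverse events by term and severity. SAP 8.4.6 summarises physical examination by body system at each visit, including children who go from normal before treatment to abnormal afterwards. Protocol 11.6.1 provides for by-subject listings and, where applicable, graphs. Failure to thrive that a clinician recognises could surface in any of these.
- The toxicity table (Protocol Appendix G) is only a heading in the text available, so whether it grades weight loss or growth is unknown.

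A reader might also infer that the conditioning is expected to impair growth. The risk section (Protocol 2.3.1) does not name growth among the busulfan risks, and Protocol 2.1.2 describes presentation of the disease, not an effect of treatment. Finally, growth is not an objective or endpoint, and 8.4.5 plans no comparison with the controls.

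All of this stands and limits the point to one table. It does not rescue that table. The other routes have no visible growth-specific rule. In a mixed-age group the minimum raw change may come from a slow-growing older child who is growing normally, while a faltering infant shows a gain.

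**Conclusion.** The point holds in limited form. Raw height and weight, with raw change pooled over a wide age range, make growth faltering or catch-up hard to detect in the 8.4.5 table, especially in infants. The 25-43% thresholds for weight and 9% for height rest on assumed CVs, a starting z-score of 0 and a fall of two SDs. They show how masking arises and do not estimate its extent in these 20 children. No primary or secondary conclusion depends on the table. This is a low-priority improvement to safety reporting. It would also bring growth into line with the SAP's own use of age-dependent ranges for immunoglobulins and lymphocyte subsets.

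**What to change.** In SAP 8.4.5, keep the raw summaries and add:

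- height-for-age and weight-for-age z-scores, specific to age and sex, from one named growth reference;
- the z-score and its change from baseline by visit, with the statistics already defined at the start of SAP Section 8;
- the number (%) of children whose z-score falls from baseline by a pre-specified amount, for example 1 or more. That figure is a suggestion, not a value from the documents.

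The cost is a paragraph of SAP text and a short derivation in the programming. The sponsor must choose and name a reference that covers infants to adolescents, and must fix the reporting threshold in advance. No new data are needed, because date of birth and sex are already used in SAP 8.2.1 and SAP 8.4.5 states that height and weight are measured over time.
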